2.1. Pressurized Olfactory Delivery (POD) Device

The Pressurized Olfactory Delivery (POD) device is intended to be used with a variety of known and yet-to-be-known drugs. The POD device is designed specifically to deliver centrally acting drugs via the olfactory and trigeminal neural pathways in the roof of the nasal cavity and olfactory nasal epithelium.

Commercially available aerosol nasal devices such as the LMA MAD device are not specifically engineered to facilitate nose-brain delivery, and consequently deposit most of the drug within the lower nasal cavity, resulting in suboptimal CNS penetration. Other problems associated with

traditional nasal sprays include variable aerosolized product, dependence on user position, and high frequency of device non-compliance/misuse. The POD device has specifically been developed to effectively and consistently deliver CNS therapeutics to the brain via the nasal/olfactory pathways. The device is not currently FDA approved, but numerous studies support its role in intranasal brain delivery of radiolabeled and therapeutic compounds.

3.0. OBJECTIVES

3.1. Primary Objective

- To measure the chronic effects of IN insulin glulisine on cognition and function in subjects with aMCI and probable mild AD over a 6 month period.

3.2. Secondary Objectives

- To measure the effect of IN insulin glulisine on mood in subjects with aMCI and mild AD over a 6 month period.
- To measure the safety and efficacy of IN glulisine in aMCI and mild AD subjects with non-insulin dependent diabetes over a 6 month period.

3.3 Exploratory Objectives

- To measure the effect of IN delivery of insulin glulisine on posterior parietotemporal and cingulate/precuneus glucose metabolism in subjects with aMCI and mild AD over a 6 month period.
- To measure the chronic effect of IN delivery of insulin glulisine on AD-specific cerebrospinal (CSF) biomarkers (A β 42, tau, and phosphotau) in subjects with aMCI and mild AD over a 6 month period.
- To measure the chronic effect of IN delivery of insulin glulisine on sleep (Sleep questionnaire and ESS) in subjects with aMCI and mild AD over a 6 month period
- To measure the chronic effect of IN delivery of insulin glulisine on olfaction in subjects with aMCI and mild AD over a 6 month period.

4. ENDPOINT(S)

4.1. Primary Endpoints

- Change in global measure of cognition as measured by the Alzheimer's disease Assessment Scale-Cognitive (ADAS-Cog-13) in subjects with aMCI and mild AD between baseline and visit 7 and between baseline and visit 10.
- Change in Clinical Dementia Rating-Sum of Boxes (CDR-SOB) between screen/baseline and final assessment visit.

- Change in daily functioning as measured by the Functional Assessment Questionnaire (FAQ) in subjects with aMCI and mild AD between baseline and final assessment visit.

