7.1.11. Visit 11; Final Safety and Discharge; Fasting (Week 28)

Following procedures will be performed at this visit.

- Collect vital signs and weight.
- Complete physical and neurological exam.

- Collect concomitant medication information and record AEs/SAEs.
- Collect laboratory samples, for specific tests refer to in Table 1.
- Perform a standard 12-lead ECG.
- Administer C-SSRS.

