12.2. Statistical Analysis of Efficacy Outcomes

Previous research has shown that the primary outcomes (ADAS-Cog 13, CDR-SOB, and FAQ) to be highly correlated. Therefore, to increase power and account for this correlation, the primary analysis will be a multivariate, linear mixed-effects regression. Specifically, the change in cognition and function measures between baseline and week 12 and between baseline and week 24 will serve as the primary outcome variables. We will include intervention arm, intervention week, intervention arm*week, age, and baseline test scores as fixed effects. The efficacy of intranasal (IN) insulin on cognition and function will be tested on the intervention arm*week interaction. Age and baseline test scores are included because of the possibility of unequal baseline values. Random intercept effects will be included to account for the nested structure of the data, multiple outcomes and observation points.

First, the assumptions of such a model will be verified. That is, the dependent variables will be tested for: (1) multivariate normality, (2) homoscedasticity, (3) equality of covariance matrices, and (4) independent observations. These outcome variables have been analyzed after log-transformation in previous studies because they have a distribution skewed to the right. We will confirm that this transformation is suitable for our study. If outcome variables are log-transformed, efficacy measures will correspond to percent change of cognitive outcomes.

To protect against type I error, efficacy of IN insulin will be considered if an overall cognitive decline is observed relative to placebo. Efficacy measures for composite cognitive and functional decline with corresponding 95% confidence intervals and p-values will be reported.

For the analysis of secondary cognition and function measures (Digit Span, Trailmaking, COWAT, Animal Naming, and WMS), secondary mood measure (GDS), and exploratory smell measure (AST) we will follow the same approach as for the primary outcomes. We have not included these tests as primary endpoints because they measure more specific effects of AD language, memory, mood, or olfaction impairment and, therefore, may be less sensitive to overall cognitive change in MCI/AD patients. Each outcome measure will be tested in its own linear mixed-effects regression model with measures from baseline to week 12 and baseline to week 24 as the outcome variables. The efficacy of IN

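### The deciding time point is not fixed: 4.1 gives CDR-SOB and FAQ one undefined final visit, 12.2 and 5.1 use weeks 12 and 24 for all three primary measures, and the result depends on how week 12 enters

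*Combined protocol and SAP*

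**What the plan says.** Section 4.1 lists three primary endpoints with different time points:

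- ADAS-Cog 13: change "between baseline and visit 7 and between baseline and visit 10", that is, weeks 12 and 24.
- CDR-SOB: "Change in Clinical Dementia Rating-Sum of Boxes (CDR-SOB) between screen/baseline and final assessment visit".
- FAQ: change "in subjects with aMCI and mild AD between baseline and final assessment visit".

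Section 12.2 names the same three measures as primary outcomes but treats them alike: "the change in cognition and function measures between baseline and week 12 and between baseline and week 24 will serve as the primary outcome variables". They enter one multivariate linear mixed model with arm, week, arm-by-week, age and baseline scores as fixed effects. The test is stated as follows: "The efficacy of intranasal (IN) insulin on cognition and function will be tested on the intervention arm*week interaction". The decision rule is that "efficacy of IN insulin will be considered if an overall cognitive decline is observed relative to placebo", which names no week.

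Section 5.1 agrees with 12.2. It says that the batteries at screen/baseline, Visit 7 and Visit 10, including the functional one, serve the primary endpoint. Section 3.1 sets the objective over 6 months. Table 2 in section 7.4 schedules CDR and FAQ at Visits 2, 7 and 10 only. The power table in 12.4 names no time point.

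**The concern.** Section 4.1 yields four primary changes (two for ADAS-Cog 13, one each for CDR-SOB and FAQ). Section 12.2 yields six (three measures at two weeks). Because 4.1 spells out both visits for ADAS-Cog 13, its single visit for the other two cannot be read as shorthand for both.

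The larger gap is that no section says which contrast over time is the primary result. Three candidates are open: the arm difference at week 24, some average over the two weeks, and the interaction named in 12.2. They estimate different quantities. The 6-month objective points to the first, the words overall and composite in 12.2 could be taken to suggest the second, and the stated test is the third. Two analysts following the plan could report different primary results from the same data, and the choice could be made after the data are seen.

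**Working it through.** **Inputs from the documents.** 45 per arm and two-sided alpha 0.05 (12.4, 12.1). FAQ difference 2, SD 3.6, power 74.100%. CDR-SOB difference 1.5, SD 1.3, power 99.972%. ADAS-Cog 13 difference 3, SD 4.6, power 88.426% (all 12.4).

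**Step 1: reproduce the printed power.** Two-sample t-test with 88 degrees of freedom and noncentrality d / (s × √(2/45)), where √(2/45) = 0.2108.

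- FAQ: 2 / (3.6 × 0.2108) = 2.635, power 74.100%. Matches.
- CDR-SOB: 1.5 / (1.3 × 0.2108) = 5.473, power 99.972%. Matches.
- ADAS-Cog 13: 3 / (4.6 × 0.2108) = 3.094, power 86.426%. The table prints 88.426%, exactly 2 points more, so that row should be checked separately.

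The two matching rows are therefore single two-group comparisons, one per outcome, and not the two-visit multivariate model of 12.2.

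**Step 2: the three contrasts.** Let d be the week-24 effect, f × d the week-12 effect, s a common SD at both weeks, and r the correlation between the two changes.

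- Week 24 alone: effect d, SD s.
- Average of both weeks: effect d(1 + f)/2, SD s√((1 + r)/2).
- Arm-by-week interaction: the outcomes are already changes from baseline, so with two weeks this term is the week-24 arm difference minus the week-12 arm difference. Effect d(1 − f), SD s√(2(1 − r)).

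The documents do not give f or r, so both are varied. The printed difference and SD are taken to describe the week-24 change, which 12.4 does not say. Each outcome is taken alone, without covariate adjustment or dropout.

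**Worked example.** FAQ, f = 0.5, r = 0.5:

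- Average: effect 1.5, SD 3.6 × √0.75 = 3.118, noncentrality 1.5 / (3.118 × 0.2108) = 2.28, power 61.7%.
- Interaction: effect 1, SD 3.6 × √1 = 3.6, noncentrality 1 / (3.6 × 0.2108) = 1.32, power 25.6%.

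**FAQ power (%); week 24 alone is 74.1 in every row.**

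| Week-12 effect as share of week 24 | Contrast | r = 0.3 | r = 0.5 | r = 0.7 | r = 0.9 |
|---|---|---|---|---|---|
| 0 | Average | 36.6 | 32.5 | 29.3 | 26.7 |
| 0 | Interaction | 59.6 | 74.1 | 92.0 | >99 |
| 0.5 | Average | 67.9 | 61.7 | 56.4 | 51.8 |
| 0.5 | Interaction | 19.6 | 25.6 | 39.1 | 83.0 |
| 1 | Average | 89.8 | 85.3 | 80.7 | 76.2 |
| 1 | Interaction | 5.0 | 5.0 | 5.0 | 5.0 |

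**The other two measures, f = 0.5, r from 0.3 to 0.9.**

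- CDR-SOB: 99.9% to 98.6% for the average and 63% to above 99% for the interaction, against 99.97% at week 24.
- ADAS-Cog 13: 81% to 65% for the average and 25% to 93% for the interaction, against 86.4% at week 24.

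With f = 1 the interaction effect is zero for every measure, so its power equals alpha.

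**The case against.** The strongest reply is that 12.2 is the operative statistical section and 5.1 agrees with it. That leaves 4.1 as the outlier, and adding Visits 7 and 10 to its CDR-SOB and FAQ lines would reconcile the text without touching ADAS-Cog 13, on which 4.1 and 12.2 already agree. As far as the list of outcomes goes, that is right. It still leaves open which contrast decides the trial.

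The reply also removes several stronger readings that a reader might infer:

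- *That the plan dilutes the 6-month effect by averaging in week 12.* Section 12.2 names the interaction and does not state an average over weeks. Averaging also need not cost power: with the full effect present at week 12 it raises FAQ power above 74.1%. The averaging figures show one possible reading only.
- *That the final assessment visit is Visit 11 (week 28), where there would be no data.* Visit 11 has the word final in its title, but it is a safety and discharge visit with neither CDR nor FAQ. The only workable reading is Visit 10.
- *That it means the last visit attended, with week-12 values carried forward for dropouts.* No section mentions carrying values forward. Section 12.1 specifies mixed models on all available observations under missing at random, and 5.2 continues follow-up after treatment is stopped.
- *That six primary changes mean six separate tests.* Section 12.2 fits one multivariate model.

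**Conclusion.** The point holds as an inconsistency in the definition of the primary endpoint and as an unspecified primary contrast. The list of primary changes differs between 4.1 and 12.2, the visit named for CDR-SOB and FAQ is undefined, and no section says which week decides a 6-month objective.

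The consequence is sensitivity to an unfixed choice, not a demonstrated loss of power. Across the assumed range, FAQ power runs from 27% to 90% under averaging and from 5% to above 99% under the interaction, against 74% for the week-24 difference. CDR-SOB is barely affected by averaging under the half-effect assumption, but the interaction has 5% power for it too if the full effect is present by week 12. All these figures rest on equal SDs at both weeks, on time courses and correlations that the documents do not give, and on univariate tests. The power of the multivariate test in 12.2 cannot be derived from what is printed.

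**What to change.** Three linked changes:

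1. Use the same list of primary changes in 4.1, 5.1 and 12.2.
2. In 4.1, replace the undefined final visit with Visit 10 (week 24), the last visit at which CDR and FAQ are collected.
3. In 12.2, state that the primary test is the arm difference in change at week 24, estimated from the mixed model, with week 12 kept in the model as supportive. This step is essential: renaming the endpoint while leaving the interaction as the tested term would not make the week-24 difference the quantity tested.

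The power table in 12.4 should then be tied to that contrast.

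No visit, assessment or sample size changes. The cost is more than editorial in one respect: the week-12 ADAS-Cog 13 change, which 4.1 and 12.2 both make primary now, becomes supportive. The change should be made before anyone has seen unblinded data.

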4.2. Safety

- Incidence and severity of serious adverse events (SAEs) and adverse events (AEs).
- Frequency of change in clinically-significant vital signs, physical exam or neurological exam.
- Change from baseline in 12-lead ECG.
- Plasma glucose level <70mg/dl.

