This study will also include a subsample of subjects with non-insulin dependent diabetes. Studies have shown that diabetics have twice the risk of Alzheimer's disease (35) and FDG-PET scans demonstrate a pattern of hypometabolism resembling Alzheimer's disease (12). We hypothesize that the subjects with peripheral deficits in insulin signaling will also be the ones to demonstrate deficits in central nervous system signaling. While diabetics comprise a significant portion of patients with AD, previous studies have excluded this population due to concerns regarding hypoglycemia in the setting of concomitant oral hypoglycemics or intranasal insulin. However, studies in non-diabetic subjects have failed to reveal any significant glucose lowering effects of IN insulin. There are minimal investigations addressing the effect of intranasal insulin on peripheral glucose in non-insulin dependent diabetes. One of the secondary objectives of this clinical trial is to demonstrate the safety and efficacy of IN glulisine in this population. Based on the multiple trials failing to reveal effects on peripheral glucose, we suspect that IN insulin will be well-tolerated in this population.

Finally, investigations have shown that Alzheimer's disease is characterized by the co-existence of cerebral amyloidosis with neurodegeneration, and that biomarkers of these abnormal changes can be used to support an AD diagnosis as well as longitudinally track disease progression (36). Most recent AD clinical trials have included biomarkers from CSF and FDG-PET to provide evidence for biological drug actions related to amyloidosis and neurodegeneration (37, 38).

2. Summary of Device Description

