7.3.3. Vital Signs

Vital signs will be recorded at all visits. For within subject consistency, brachial artery pressure will be obtained in the routine fashion, the same arm should be used for all study measurements.

Blood pressure and heart rate to be measured after subject has been sitting quietly for a minimum of 5 minutes. Diastolic blood pressure will be measured at the disappearance of Korotkoff sounds. Vitals sign will be monitored by clinical staff during each visit of the study.

In addition, vital signs will be measured pre and post study dose on Visits 3 and 4. The investigator will be notified for any baseline changes in blood pressure >20 mmHg systolic and >10 mmHg diastolic

A pre-dose fingerstick blood glucose will be measured followed by measurements post- study drug at 15 minute, 30 minute and 1 hour during visit 3 and 4. The investigator will be notified for any baseline changes. A blood glucose < 70 mg/dL will be considered clinically significant.

Vital signs will be taken prior to ECG and blood draw.

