7.3.6.1 HOMA-IR – Measure for Insulin Resistance

Calculation of HOMA-IR with Blood glucose and insulin level during Visit 1 using the following formula(45, 46);

$$\text{HOMA-IR} = [\text{glucose (nmol/L)} * \text{insulin } (\mu\text{U/mL})/22.5]$$

See **Table 1** for specific list of laboratory assessments.

Table 1 Laboratory Assessments

Procedure	Visit 1;	*Visit 3;	*Visit 4;	Visit 11;	Early Withdrawal
Basic Metabolic Panel (Na, K, CO ₂ , Cl, BUN, Creatinine, Glucose and Ca)	X		X	X	X
Insulin Level	X			X	X
CBC w/ Diff	X			X	X
Fingerstick Blood Glucose Baseline, post study dose, 15 min, 30 min and 1hour		X	X		
HbA1c	X				
APOE status	X				
Thyroid Stimulating Hormone (TSH)	X				
Vitamin B12	X				

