12.3. Statistical Analysis of Safety Outcomes

Adverse event rates will be modeled using Poisson regression with a natural logarithm link function. If over dispersion is identified, a negative binomial model will be used instead. Incidence rate ratios and 95% confidence intervals will be reported. Differences in baseline to 3-month and 6-month change in vital signs and 12-lead ECG will be assessed using Student’s two-sample t-test.

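### Glucose is listed only as a yes/no value below 70 mg/dl, and no between-arm comparison of the serial glucose readings is planned; the count is a weak measure of glucose lowering, above all in diabetics

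*Combined protocol and SAP*

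**What the plan says.** Section 4.2 (Safety) gives glucose one line: "Plasma glucose level <70mg/dl". The ECG item in the same list is framed as change from baseline; the glucose item is not.

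Section 7.3.3 (Vital Signs) sets out the serial readings at Visits 3 and 4: "A pre-dose fingerstick blood glucose will be measured followed by measurements post- study drug at 15 minute, 30 minute and 1 hour". That gives two pre-dose and six post-dose values per subject. The same section states that "A blood glucose < 70 mg/dL will be considered clinically significant", and about other movements it says only that "The investigator will be notified for any baseline changes". The introduction to the study assessments makes every visit non-fasting unless marked otherwise, and Visits 3 and 4 are not marked.

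Table 1 holds a second source of glucose: "Basic Metabolic Panel (Na, K, CO ₂ , Cl, BUN, Creatinine, Glucose and Ca"), drawn at Visits 1, 4 and 11 and at early withdrawal.

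Section 12.3 models adverse event rates by Poisson or negative binomial regression. Its only continuous comparison is this: "Differences in baseline to 3-month and 6-month change in vital signs and 12-lead ECG will be assessed using Student’s two-sample t-test". Glucose is not named.

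Section 1.1 gives the reason for including diabetics: "There are minimal investigations addressing the effect of intranasal insulin on peripheral glucose in non-insulin dependent diabetes". Section 3.2 makes safety in non-insulin dependent diabetes a secondary objective, and Section 8.3 stratifies randomization by it.

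**The concern.** The trial raises the question of what intranasal glulisine does to peripheral glucose in diabetics and collects randomized, blinded, quantitative readings around two doses. The listed endpoint records only whether a value falls below 70 mg/dl. A subject who starts at 150 mg/dl and falls by 30 is at 120 and counts the same as one who did not move.

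The fingersticks sit under the vital signs heading, but that does not bring them into the analysis. The t-test in Section 12.3 is for change at 3 and 6 months, and no fingerstick is scheduled then.

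With no prespecified estimate of glucose change, few values below 70 in either arm would say little about whether glucose moved. Any later look at the serial readings would be post hoc.

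**Working it through.** **The plan's own figures.** The documents give no power or precision figure for glucose. The only power figures (Section 12.4, 45 per arm, two-sided 0.05) are for the three primary outcomes. A two-sample noncentral-t calculation gives 86.43%, 99.97% and 74.10%, against the stated 88.426%, 99.972% and 74.100%. The last two match. The first is about 2 points off, which does not bear on this point. The same type of calculation is used below.

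**Inputs from the documents.** 45 per arm; two-sided 0.05; six post-dose readings per subject.

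**Assumed inputs (none in the documents).**
- All subjects: pre-dose mean 105 to 115 mg/dl, SD 15 to 20.
- Diabetics: pre-dose mean 150, SD 35, with 10 or 20 per arm.
- SD of a single change reading, s: 15, 20 or 25 mg/dl, half the variance between subjects and half between readings.
- Pre-dose values floored at 75 mg/dl; one pre-dose level per subject.
- A constant true fall in the active arm.

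**Mean change.** The SD of a subject's mean of six changes is s × √(0.5 + 0.5/6) = 0.764 s. The standard error of the arm difference is 0.764 s × √(2/n). For s = 20 and n = 45 this is 15.28 × 0.2108 = 3.22 mg/dl. A 10 mg/dl fall then has noncentrality 10/3.22 = 3.10 and power 86.7%.

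**Count.** The chance that any of six readings is below 70 was simulated per arm, and exact Fisher power was computed from the two proportions. Examples:
- All subjects, mean 105, s = 15, 10 mg/dl fall: 13.3% versus 27.6% of subjects, power 29%.
- All subjects, mean 115, s = 25, 10 mg/dl fall: 21.7% versus 33.1%, power 16%.
- Diabetics, 20 per arm, s = 25, 15 mg/dl fall: 7.8% versus 14.8%, power 4%.

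| Group | True fall (mg/dl) | Count below 70 | Mean change |
|---|---|---|---|
| Diabetics, 10 per arm | 10 | under 1% | 20–46% |
| Diabetics, 10 per arm | 15 | under 1% | 38–79% |
| Diabetics, 20 per arm | 10 | 0–2% | 37–77% |
| Diabetics, 20 per arm | 15 | 1–4% | 68–98% |
| All, 45 per arm | 10 | 16–29% | 69–98% |
| All, 45 per arm | 15 | 37–66% | 96% or more |
| All, 45 per arm | 20 | 63–92% | over 99% |

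At 10 per arm the count can hardly succeed. With no events in one arm, Fisher's test needs 5 in the other: 2 × C(10,5)/C(20,5) = 2 × 252/15504 = 0.033, whereas 4 gives 2 × 210/4845 = 0.087.

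**Sensitivity.**
- Drawing the two pre-dose values independently, which favours the count, raises it to 22–41% (10 mg/dl) and 47–81% (15 mg/dl) in all subjects, and to at most 7% in diabetics at 10 to 15 mg/dl.
- A separate model with within-subject SD 12 and diabetic means of 140 to 160 gives the count 1–20% for a 10 to 20 mg/dl fall even if all 45 per arm were diabetic.
- In that model's non-diabetics starting near 100 to 105 mg/dl (within-subject SD 8), a 15 to 20 mg/dl fall is detected with about 71% to over 99% power.

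**Precision of mean change.** The 95% half-width is t × 0.764 s × √(2/n), for s = 15, 20, 25:
- n = 45 (t = 1.987): 4.8, 6.4, 8.0 mg/dl.
- n = 20 (t = 2.024): 7.3, 9.8, 12.2 mg/dl.
- n = 10 (t = 2.101): 10.8, 14.4, 17.9 mg/dl.

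By contrast, zero events in 45 leaves a one-sided 95% upper limit of 1 − 0.05^(1/45) = 6.4% for the event rate and puts no bound on the shift in glucose.

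**The case against.** The count fits a safety purpose. Section 1.1 says earlier trials left diabetics out because of concern about hypoglycaemia, and a value below 70 addresses that directly. This stands: the gap is the missing continuous companion, not the cut.

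Glucose is not otherwise ignored. Investigators are notified of changes, clinically significant findings become adverse events and enter the rate model, and Section 12.1 promises central tendency and spread by arm for each outcome variable. All true, but none of it is a prespecified between-arm comparison of change from pre-dose.

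Section 12.3 names no test for the count, so Fisher's test on any of six readings is this review's choice. The percentages illustrate how little the cut retains; they are not the power of a planned test.

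The continuous estimate may also disappoint in diabetics. Their number is not stated, and their readings may vary more at non-fasting visits. If s were 40 (an assumption), power for a 10 mg/dl fall would be about 17% with 20 per arm and 11% with 10. This stands too, but an interval shows such imprecision where a count of zero hides it.

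A reader might infer that a glucose-lowering effect would almost always be missed. Across the whole trial that does not hold: under these assumptions a 15 mg/dl fall is detected 37–66% of the time and a 20 mg/dl fall 63–92%. A reader might also take the endpoint to be derived from the serial readings. Section 4.2 says plasma, the serial readings are fingersticks and panel glucose is also drawn, so the source is undefined.

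**Conclusion.** The point holds in limited form. The only listed glucose endpoint is a cut at 70 mg/dl of unstated source, and no between-arm analysis of glucose is planned although suitable readings are collected. In diabetics the cut has about 0–4% power for a 10 to 15 mg/dl fall, against about 20–98% for mean change. In all subjects it has about 16–29% against 69–98% at 10 mg/dl, and 37–66% against 96% or more at 15 mg/dl.

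Every glucose mean, SD, fall and diabetic count behind these figures is assumed. The direction is stable over the ranges tried; the exact percentages are not. The simulated placebo arm has about 9–31% of all subjects with a reading below 70; lower true rates would generally leave the count weaker still.

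Two further inferences are not supported. The documents do not plan to conclude from the count that glucose is unaffected. Nor would the collected data bound the effect tightly in diabetics: the ±5 to ±8 mg/dl precision is for the whole trial. This is a cheap improvement to a safety analysis and does not touch the primary endpoints.

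**What to change.** - **Section 4.2:** keep the count below 70 mg/dl and state its source (fingerstick, panel or both, and which visits). Add change from pre-dose fingerstick glucose at 15, 30 and 60 minutes, Visits 3 and 4.
- **Section 12.3:** state how the count will be compared. Add one linear mixed model of post-dose glucose with fixed effects for arm, minute, visit, that visit's pre-dose value, diabetes status and arm-by-diabetes, and a random subject effect.
- **Reporting:** give the arm difference with its 95% interval overall and in diabetics, labelled as estimation without a multiplicity claim. Base any statement about peripheral glucose on that interval.

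Expected half-widths are about ±5 to ±8 mg/dl overall, ±7 to ±12 with 20 diabetics per arm and ±11 to ±18 with 10; say in advance that the diabetic estimate may be imprecise. The estimate covers the hour after a dose in the first week. The Visit 4 pre-dose value already follows a week of treatment, so the model does not measure a sustained effect.

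Cost: a few lines, one model and one more safety estimate to report. No new visit, sample or subject is needed.
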